 - b. Intrinsic Motivation Inventory (IMI) Interest and Enjoyment Subscales¹⁴
 - c. Participant compliance with exercise will be tracked as number of exercise sessions missed/possible sessions.
5. Healthcare Use:

- a. Number of healthcare provider visits scheduled and attended; from electronic medical record.
- b. Number of hospital contacts (emergency department visits and hospital admissions); from electronic medical record.

Interventions and Duration

Forty-four participants will be randomly assigned to two groups: 1) experimental (EXP) or 2) control (CTL). The entire intervention period is 12 weeks, with the primary end point at 12 weeks. At 24 weeks after initiation of intervention, each group will be asked to return for a follow-up test session.

Evaluations will take place using the following schedule:

Baseline, 12 and 24 weeks: Physical Performance Tests, Self-Report Physical Function Measures, Activity Measurement, Self-Efficacy questionnaire, Motivation questionnaire, Health Status questionnaire, and healthcare use assessment.

Baseline only: At Baseline testing, participants will also complete the following tests/measures/forms: 1) Folstein Mini-Mental State Examination,¹⁵ 2) Geriatric Depression Scale SF,^{16,17} 3) Chakrabarty scoring of residual-limb quality,¹⁸ 4) Residual limb length, 5) lower extremity sensory testing, 6) pre-amputation ambulatory status report, 7) type of prosthesis (socket, suspension, and foot), and 8) demographic information. Hemoglobin A1c measurements (for DM) and confirmation of PAD will be extracted from the participant medical records.

Continuously: Falls, Adverse Events (AEs), and Serious Adverse Events (SAEs) will be recorded and reported as needed.

Sample Size and Population

The target sample is 44 persons with recent transtibial amputation, resulting from PAD or DM complications.

Participants will be recruited from the University of Colorado Hospital and Denver Health.

Title: Collaborative-care rehabilitation to improve functional outcomes after dysvascular amputation

A. Abstract & Specific Aims

The primary objective of this project is to determine the efficacy of a collaborative-care, home-based exercise program for improving physical function, activity level, and health self-management within the first year following dysvascular transtibial amputation.

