 - (1) H3: The rehabilitation program group will tend to have greater positive change in ratings on the Self-Efficacy in Managing Chronic Disease (SEMCD) questionnaire and Intrinsic Motivation Inventory (IMI) Interest and Enjoyment Subscales, compared to the standard of care group at 12 and 24 weeks following initiation of intervention.
 - (2) H4: The rehabilitation program group will tend to have higher numbers of attended healthcare provider appointments and lower numbers of hospital contacts at 12 weeks and 24 weeks, compared to the standard of care group.

2. Exploratory Aim 2 (EA2) and Hypothesis (H4) are:

- a) EA2: Identify factors predictive of physical activity level and disability measured by activity monitors and self-reported disability (World Health Organization Disability Assessment Schedule 2.0), respectively.
- b) H5: Significant predictors of physical activity and disability will be identified from the categories of demographic/anthropometric, activity/mobility, health behaviors, physical health, amputated-limb health, contralateral-limb health, cognitive/affective health, and healthcare use factors for participants at 24 weeks following intervention, regardless of group assignment.

B. Background and Significance

B1. Significance. Limitations in physical function are common following dysvascular major lower limb amputation.^{28,29,31} This is a significant issue considering that dysvascular amputation is becoming increasingly more common in the United States. Dysvascular amputation is operationally defined as amputation resulting from severe PAD with critical limb ischemia or severe DM with dense distal sensory and motor neuropathy leading to a non-healing wound (or a combination of these two related, but separate pathophysiologies). The projection of 2.3 million people living with amputation in the United States by the year 2050 represents an increase of nearly 100% from current values.¹⁹ As a result, dysvascular amputation has become a major healthcare issue in the U.S, including an economic problem.³²

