Health self-management will be promoted in 3 primary ways: 1) action plan development with participant-directed goal setting, 2) participant self-tracking of activity (pedometers and exercise diary), and 3) participant education on problem-solving skills to manage chronic health conditions. Participants will also monitor their individual health condition (e.g., heart rate, time to claudication with walking, blood sugar, and blood pressure). These data will focus the weekly discussions (home or phone) over the 12-weeks.^{44,66,67}

Control (CTL) Group: CTL group participants will be contacted at the same interval (phone and home visits) as the EXP group (Figure 2) to ensure attention control between groups. Visits will

Table 3. EXP Group Rehabilitation Program

Category	Specific Components
Impairment-Based Exercise	
A. Strengthening* (3x/week)
 
Hip Extensors Hip Abductors Hip Adductors Knee Extensors Knee Flexors Ankle Plantar Flexors (intact limb) Trunk Stabilization
 
B. Stretching (3x/week)
 
Hip Flexors Knee Flexors

Activity-Based Intervention	• Walking Program (3x/week)
Health Self-Management	
 • Participant-tailored goals • Participant self-tracking of exercise and activity • Participant education on problem-solving skills for managing health

* List of options for strengthening program, priority muscles to be included in the program based on patient-researcher collaboration, with input from primary PT.

consist of recording problems reported by the participant. If health or rehabilitation questions arise that require professional advice during participant-researcher visits, the participant will be referred to his/her healthcare provider.

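### Study contacts are matched in frequency but not in content, and no common procedure for eliciting falls and adverse events is stated, so event tabulations by arm and the exploratory H4 visit count can pick up procedural differences

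*Protocol*

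**What the plan says.** **EXP contacts (protocol D4).** Participants are phoned weekly about progress, barriers and new goals. They track activity with a pedometer and diary, and monitor heart rate, claudication time, blood sugar and blood pressure. The protocol adds: "These data will focus the weekly discussions (home or phone) over the 12-weeks".

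**CTL contacts (protocol D4).** "CTL group participants will be contacted at the same interval (phone and home visits) as the EXP group", as an attention control. The visits "consist of recording problems reported by the participant". Then: "If health or rehabilitation questions arise that require professional advice during participant-researcher visits, the participant will be referred to his/her healthcare provider". The EXP text contains no corresponding sentence.

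**Harms (protocol synopsis, Interventions and Duration).** Under continuous evaluations: "Falls, Adverse Events (AEs), and Serious Adverse Events (SAEs) will be recorded and reported as needed". This does not distinguish the arms and gives no question, script or schedule for eliciting events. Neither D5 nor the SAP names a comparison of adverse events between arms.

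**Healthcare use (protocol synopsis, Design and Outcomes, item 5).** The measure is "Number of healthcare provider visits scheduled and attended; from electronic medical record"; hospital contacts have the same source. H4 expects the EXP group to show "higher numbers of attended healthcare provider appointments and lower numbers of hospital contacts at 12 weeks and 24 weeks". The protocol calls the aim containing H4 exploratory and probably under-powered. D5 nevertheless lists visit and hospital-encounter counts among the secondary analyses at 12 weeks, analysed as the primary outcome is, and the SAP model covers all outcomes.

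**The concern.** Equal contact frequency controls for attention. It does not equalise what is looked for at a contact, or what the text says happens when something is found.

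For harms, a contact built around a diary and a set of readings may bring up a different share of falls and minor events from one that records what the participant reports. Without a common elicitation procedure, counts by arm depend partly on how each arm is observed. That cannot be repaired once the contacts have taken place. It matters here because the EXP programme raises walking and exercise load at home in people with a recent amputation, so a reader of the results will want falls and events shown by arm.

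For H4, a visit that follows a study referral looks like any other visit in the medical record. If the arms generate such visits at different rates, the count reflects trial procedure as well as the programme. The protocol intends trends under this aim to inform the power calculation for a later study, so the distortion could carry forward.

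**Working it through.** **Figures in the plan.** The only design calculation is the TUG sample size in D6: difference 6.0 s, SD 6.0 s, 80% power, 17 per group. At a two-sided 5% level (sidedness is not stated), exact t-test power is 0.781 with 16 and 0.807 with 17 per group, so the stated figure reproduces. It does not enter this point, and nothing below changes it.

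**Passages side by side.**

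| | EXP | CTL |
|---|---|---|
| Contact interval | Weekly phone contact, plus home visits | Same |
| Stated content | Progress, barriers, goals, self-monitored data | Problems reported by the participant |
| Health readings kept | Yes | None stated |
| Referral statement | None | Yes, conditional |
| How falls and events are elicited | Not stated | Not stated |
| Source of visit counts | Medical record | Medical record |

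Rows 2 to 4 differ in the text. Row 5 is open in both arms.

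**Illustration 1: ascertainment.** The documents give no detection rates, so these are assumptions. With the same true risk p in both arms and detection shares d_E and d_C, the apparent ratio is (p × d_E)/(p × d_C) = d_E/d_C, whatever p is.

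- 80% and 70%: 0.80/0.70 = 1.14
- 80% and 50%: 0.80/0.50 = 1.60
- 50% and 80% (the reverse): 0.50/0.80 = 0.63

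For scale, take 22 per arm (44/2) and an assumed true risk of 40%. Then 22 × 0.40 = 8.8 participants per arm have an event. Detection of 80% and 50% shows 7.0 against 4.4, a gap of 2.6 participants with no true difference.

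**Illustration 2: provider visits.** Let D be the true EXP excess in attended visits, and r_E and r_C the study-prompted extra visits per participant. The observed excess is D + r_E − r_C. Assume 12 contacts (one a week for 12 weeks), each prompting an extra attended visit with probability 2%, 5% or 10%:

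- 12 × 0.02 = 0.24
- 12 × 0.05 = 0.60
- 12 × 0.10 = 1.20

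If referrals arose in CTL only (r_E = 0), a true excess of 1 visit would be observed as 0.76, 0.40 or −0.20, and an excess of 2 as 1.76, 1.40 or 0.80. If EXP contacts prompted visits at 10% and CTL contacts at 2%, the shift would be 1.20 − 0.24 = +0.96, the other way.

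These figures are upper values for each assumed rate. They take every referral to become an additional attended visit that reaches the record, and they apply to all contacts a sentence that mentions visits.

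**The case against.** The strongest reply is that the protocol leaves a detail open and contradicts nothing. Much of it stands.

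- **No comparison of adverse events between arms is planned.** This is correct. The point applies only to whatever tabulation by arm is produced.
- **The CTL wording does not say that staff wait for problems to be volunteered.** A reader might infer this, but the sentence says what is recorded, not whether staff ask. A contact devoted to recording problems could surface as many events as a goal-setting call, so it is not established that EXP detects more.
- **Referral in CTL is conditional.** It applies to questions that need professional advice, and it plausibly serves to keep researchers from treating controls. The text does not say that CTL problems in general are sent out.
- **Silence about EXP is not evidence that EXP participants are not referred.** A reader might infer that a worrying reading in EXP has no route to care. The documents do not support that. They do not state the handling, and Figure 2, cited for the contact schedule, is not available to this review.
- **Visit counts come from the medical record.** Detection at study contacts therefore does not bias them directly. Only visits caused by a referral matter. Visits prompted by EXP self-monitoring are arguably part of the programme's effect.
- **A shift from CTL referrals alone would work against H4.** It would not produce a false finding in favour of H4.

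What the reply does not remove is that the stated content of contacts differs by arm while no common elicitation procedure is given. Recording events continuously in both arms does not make ascertainment equal.

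**Conclusion.** The point holds as a risk to interpretation. Followed as written, D4 allows ascertainment of falls and adverse events to depend on arm, and it allows study-prompted visits to enter the H4 provider-visit count unequally.

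A reader might go further and conclude that the comparison of adverse events is biased, or that the H4 estimate is pulled against its hypothesis. Neither follows: the first comparison is not planned, and the net sign of the second depends on prompting in EXP, which the documents do not describe.

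The size is unknown. The ratios of 1.14 and 1.6 (or 0.63 in reverse) and the shifts of 0.24 to 1.2 visits rest wholly on assumed detection and referral rates. They show only that modest procedural differences could matter with 22 per arm. H4 is exploratory, and the primary TUG comparison is untouched. This is a cheap improvement to make before contacts begin, because ascertainment cannot be equalised afterwards.

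**What to change.** 1. In D4, open every phone or home contact in both arms with the same scripted questions on falls, new problems, emergency department visits and admissions, before any discussion of goals or readings.
2. Record how each event was found: script, EXP self-monitoring or medical record. Base any tabulation by arm on events found by the script or the medical record. List events found only through EXP self-monitoring separately, so that they are still reported.
3. Log each study-prompted referral in both arms. Report H4 provider visits with and without the resulting visits, as a sensitivity analysis. Keep the full count as well, since visits arising from EXP self-monitoring may be part of the programme's effect.
4. The sponsor should reconcile the EXP and CTL passages on referral so that the handling in each arm is stated. No clinical rule is proposed here.

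**Cost.** A one-page script, two database fields, some protocol wording and slightly longer contacts, with a small and equal increase in attention in both arms. Sample size, programme and primary analysis are unchanged. The script will not make ascertainment perfectly equal, because participants who keep a diary may recall events better, but it removes the difference in what they are asked.

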Collaborative-Care Rehabilitation to Improve Functional Outcomes after Dysvascular Amputation

Protocol Version: January 5, 2014

COMIRB Protocol

COLORADO MULTIPLE INSTITUTIONAL REVIEW BOARD
[name] [contact] [contact]

Title: Collaborative-Care Rehabilitation to Improve Functional Outcomes after Dysvascular Amputation

Principal Investigator: [name], PT, Ph.D.
V1.3

SYNOPSIS

Objectives

The objective of this study is to determine the efficacy of a collaborative-care, home-based rehabilitation program for improving functional outcomes following dysvascular transtibial amputation. The primary aim is to determine if the rehabilitation program improves performance-based and participant-report measures of physical function, compared to standard of care, for participants with dysvascular transtibial amputation. The secondary aim is to determine if the rehabilitation program improves daily physical activity, compared to standard of care, for participants with dysvascular transtibial amputation. Two exploratory aims are: 1) determine the efficacy of the intervention for promoting health self-management, measured as participant-reported self-efficacy for managing chronic disease, motivation for exercise, and health-care resource use and 2) identify factors at initial testing that are predictive of physical activity level and disability 24 weeks after intervention.

Design and Outcomes

This will be a randomized, controlled clinical trial on the effects of 12 weeks of collaborative-care, home-based rehabilitation on physical function outcomes. Outcome variables include:

1. Performance-Based Physical Function Measures:
 - a. Timed Up-and-Go (TUG)¹
 - b. Two-Minute Walk (2MW)²
 - c. Five-meter Walk (5mW)³
2. Self-Report Physical Function Measures:
 - a. Prosthesis Evaluation Questionnaire – Mobility Section (PEQ-MS)⁴
 - b. Houghton Scale⁵
 - c. Patient-Specific Functional Scale (PSFS)⁶
3. Activity Measurement:
 - a. Physical activity monitors (Actigraph) worn for 1 week following each test session (baseline, 12-week, 24-week). These monitors are valid tools for measuring relative level of activity (e.g., sedentary, light, moderate, vigorous) for various patient populations⁷⁻⁹ and are valid and reliable spatiotemporal gait measures for patients with lower limb amputation.^{10,11}
4. Self-Efficacy and Motivation:
 - a. Self-Efficacy in Managing Chronic Disease (SEMCD) questionnaire^{12,13}

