Results of this study will quantify the effect size of the proposed intervention and inform future research designed to optimize intervention, focus examination based on the dominant pathophysiology (i.e., DM, PAD, or both), and examine efficacy in other populations (e.g., patients with trans-femoral amputation).

Specific Aim 1: The Primary Aim (PA1), on which this trial is powered, and the Primary Hypotheses (H1.1 and H1.2) are:

- a) PA1: Determine if the collaborative-care, home-based rehabilitation program improves performance-based and participant-report measures of physical function compared to standard of care for participants with dysvascular transtibial amputation.

[figure not shown]

Figure 1. Outcome factors after amputation

- b) H1.1: The rehabilitation program will result in greater improvements in the performance-based measures of the Timed Up-and-Go, 2-Minute Walk, and 5-meter Walk tests than standard of care at 12 weeks (primary end-point) and persist at 24 weeks following initiation of intervention.
- c) H1.2: The rehabilitation program will result in higher ratings of participant-reported physical function on the Prosthesis Evaluation Questionnaire – Mobility Section, Houghton Scale, and Patient-Specific Functional Scale than standard of care at 12 weeks (primary end-point) and persist at 24 weeks following initiation of intervention.

Specific Aim 2: The Secondary Aim (SA) and Hypothesis (H2) are:

- a) SA: Determine if the collaborative-care, home-based rehabilitation program improves physical activity when compared to standard of care for participants with dysvascular transtibial amputation.
- b) H2: The rehabilitation program will result in greater increases in physical activity than standard of care at 12 weeks (primary end-point) and persist at 24 weeks following initiation of intervention.

Exploratory Aims:

1. Exploratory Aim 1 (EA1) and Hypotheses (H3 & H4) are:

- a) EA1: Determine if the collaborative-care, home-based rehabilitation program influences the health self-management factors of self-efficacy for managing chronic disease, motivation for exercise, and healthcare use.
- b) While the study will likely be under-powered to find differences related to this aim, the, if trends in group differences are seen, data will provide a means for performing a statistical power analysis to determine sample size for future study. The hypothesized trends for group differences are:

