D5. Data Analysis. Data will be managed using REDCap (Research Electronic Data Capture; which is HIPAA compliant).⁶⁸ Primary analysis will be group differences in TUG times (primary outcome) at the 12-week time point. As a pilot feasibility study, data will only be analyzed for participants with sufficient intervention exposure, defined as six weeks. For participants who withdraw at or beyond six weeks of intervention, an early termination test will be performed and carried forward as the end-point. Participants who withdraw before completing six weeks will be lost to follow-up and no imputation will be performed for missing data. Attempts will be made to test all participants at 24-weeks. However, missing 24-week data will not be imputed from the 12 week measurement, as this would bias the effect following the primary end-point (i.e., it is expected that both groups would have worse 24- compared to 12-week outcomes). Group differences will be based on a linear model with TUG as the outcome and explanatory variables being primary medical diagnosis (PAD, DM, or both), rehabilitation site, treatment group, and baseline TUG. Group differences will be determined by this single test to protect against Type I error (α level: 0.05).

Secondary analyses will include differences at 12-weeks in the other outcomes (2MW, 5mW, PEQ-MS 12/5, Houghton Scale, PSFS, Activity level, number of healthcare provider visits, and number of hospital encounters) using the same method as for the primary outcome. A mixed-effects model with time as a fixed covariate across baseline, 12-, and 24-weeks will be used to evaluate long-term outcomes (24-week) and make inferences regarding the effectiveness of the intervention up to 12-weeks after intervention is complete. As with the other analyses, evaluation of the time trajectory will be conditioned on stratification variables and baseline values of the outcome measure. Also the mixed-effects model will not include data from subjects who drop prior to 6 weeks.

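### Protocol D5 restricts the primary TUG test and the 24-week model to people with six weeks of exposure, a post-randomisation filter that the SAP does not contain

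*Protocol*

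**What the plan says.** The Protocol synopsis sets an efficacy objective: "The objective of this study is to determine the efficacy of a collaborative-care, home-based rehabilitation program". Participants are randomised at the initial test session (D3).

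D5 names TUG at 12 weeks as the primary outcome, tested once at alpha 0.05, and then adds three rules:

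- Exposure: "As a pilot feasibility study, data will only be analyzed for participants with sufficient intervention exposure, defined as six weeks".
- Leaving before week 6: "Participants who withdraw before completing six weeks will be lost to follow-up and no imputation will be performed for missing data".
- Leaving at or after week 6: "For participants who withdraw at or beyond six weeks of intervention, an early termination test will be performed and carried forward as the end-point".

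The secondary 12-week outcomes follow the primary method. For the longer-term model D5 states: "Also the mixed-effects model will not include data from subjects who drop prior to 6 weeks". Yet D5 also says "Attempts will be made to test all participants at 24-weeks", and the synopsis says "At 24 weeks after initiation of intervention, each group will be asked to return for a follow-up test session". Hypothesis H1.1 covers both times: "Walk tests than standard of care at 12 weeks (primary end-point) and persist at 24 weeks following initiation of intervention".

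The SAP carries the same date. It fits one maximum-likelihood repeated-measures model per outcome to the 12- and 24-week tests, adjusted for baseline, and uses all available data under missing at random. It contains no exposure criterion, analysis set or carry-forward rule.

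**The concern.** Six weeks of exposure is known only after allocation. D4 matches the frequency of contact between arms but not its content: EXP exercises and walks, while CTL visits record problems. Equal early leaving therefore cannot be assumed. D5 also does not say what six weeks of intervention exposure means for CTL.

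If leaving is related to later TUG beyond what baseline TUG explains, and differs by arm, the estimate is biased and the single 5% test can exceed its level.

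Two analysts, one following D5 and one the SAP, could also analyse different people and use different values for the same person. A choice between the documents made after results are seen would undo the protection that D5 seeks from a single test.

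**Working it through.** **1. The plan's own figure.** D6 gives a difference of 6.0 s and SD 6.0, so d = 1.0. A two-sided two-sample t-test at 0.05 needs 16.7, so 17 per arm, with power 80.7%. Allowing 20% loss, 17/0.8 rounds up to 22 per arm, or 44. The sample size reproduces and is not at fault. The plan tolerates 44 − 34 = 10 losses.

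**2. Where the two documents differ.**

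| Person | D5 | SAP |
|---|---|---|
| Under 6 weeks, baseline only | excluded | adds nothing (baseline is a covariate) |
| Under 6 weeks, tested at 12 weeks | excluded | included |
| Under 6 weeks, tested at 24 weeks only | excluded | included at 24 weeks, and informs the 12-week estimate through the joint model |
| Leaves at or after week 6 | early test carried forward | no such rule |

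D5 does not say whether withdrawing means stopping the intervention or leaving the study, so the second and third rows cannot be ruled out.

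**3. Hand calculation.** If the excluded have TUG worse than the retained by g seconds in both arms, and fractions fE and fC are excluded, the EXP − CTL difference shifts by −g(fE − fC). Here g is assumed to run from 3.4 s (D6's minimal detectable change) to 6.0 s.

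- 5 of 22 EXP, 0 of 22 CTL: 3.4 × 5/22 = 0.77 s to 6.0 × 5/22 = 1.36 s. The standard error is 6 × √(1/17 + 1/22) = 1.94 s, and type I error is 6.7% to 10.5%.
- 3 against 0: 0.46 to 0.82 s, type I error 5.7% to 7.1%.
- 3 against 3: 0.

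**4. Simulation with baseline adjustment.** The setting has 22 per arm, SD 6.0, no true effect and ANCOVA on group and baseline. Assumptions: baseline to 12-week correlation 0.5 to 0.7; 12- to 24-week correlation 0.8; leaving score correlated 0.3 to 0.7 with worse 12-week TUG; 6 EXP and 2 CTL leave early. Each setting has 20,000 trials. Negative values favour EXP.

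| Setting | Bias (s) | Type I error |
|---|---|---|
| 12 weeks, early leavers absent (D5 and SAP alike) | −0.25 to −0.89 | 5.5–9.3% |
| 12 weeks, half tested and included | −0.09 to −0.34 | 5.2–5.7% |
| 12 weeks, all tested and included | 0 | about 5% |
| 24 weeks, all tested, D5 drops them | −0.20 to −0.72 | about 5% to 7.5% |
| 24 weeks, all tested, SAP keeps them | 0 | about 5% |
| 24 weeks, half tested, SAP | −0.08 to −0.28 | not tabulated |
| 12 weeks, all tested at 24 weeks only, SAP joint model | −0.13 to −0.41 | bias only |

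Other splits, with early leavers absent at 12 weeks:

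- 3/1 gives −0.13 to −0.48 s (5.0–6.8%).
- 2/6 reverses the sign at about the same size.
- 4/4 gives bias near 0 and type I error of 5.2–6.3%.

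**5. Carry-forward.** D6 assumes CTL declines. If it worsens by 6.0 s linearly over 12 weeks (assumed), a test at week w reads 6 × (1 − w/12) below the week-12 value: 3.0 s at week 6 and 0.5 s at week 11. Two such people among 20 CTL move the CTL mean by 3.0 × 2/20 = 0.30 s or 0.5 × 2/20 = 0.05 s, which shrinks the group difference. D5 declines to carry 12-week values to 24 weeks because expected decline would bias the result. The same argument applies to its own carry-forward to week 12.

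**The case against.** The strongest reply is that at the primary end-point the documents do not differ on the ordinary reading. An early leaver has no 12-week test, and a baseline-only participant adds nothing to the SAP contrast. **This stands.** The 12-week figures measure absence, not D5's wording, and rewording alone removes none of that bias.

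The 24-week divergence also needs an early leaver to return. That is true, but the Protocol plans to attempt it. D5 places the 24-week model among its secondary analyses, which limits the consequence, although persistence is part of H1.1.

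The SAP could be read as operating inside D5's set, with its phrase about available data describing only how likelihood handles gaps. That reading is possible, but nothing in either document states it.

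The 6/2 illustration is pessimistic. D6 implies five losses per arm, and it describes its loss rate as twice that seen in comparable 12-week studies. Removing a fixed number of top-ranked people also adds to type I error: with independent leaving at the same expected rates, the 9.3% extreme falls to about 8.2%, and the 4/4 case to 4.3–5.4%. These points stand, and they reduce the illustration without touching the rule.

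A set requiring a post-baseline test is itself known only after randomisation. That is also true, and it relies on missing at random. It does, however, discard no observed outcome, and continued testing keeps it close to everyone randomised.

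Finally, D5 gives pilot feasibility as its reason, and the SAP calls the study early phase. The stated objective is nonetheless efficacy, with one test at 0.05.

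**Conclusion.** The concern holds and must be fixed before analysis. D5 imposes a post-randomisation exposure filter on the primary and 24-week analyses, the SAP does not, and neither document takes precedence. Late leavers' 12-week value is also unreconciled, as a secondary matter.

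The severity rests on the rule and the unsettled analysis set, not on a demonstrated bias. Under assumed early leaving the shifts are fractions of a second up to about 0.9 s in the adjusted simulation (1.36 s in the harshest hand calculation), against a planned 6.0 s. They could go either way and vanish when leaving is balanced. The number, split and TUG of early leavers are not in the documents.

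**What to change.** 1. State one primary analysis set in both documents: all randomised participants with at least one 12- or 24-week measurement, in their allocated arm whatever their exposure, analysed with the SAP's maximum-likelihood model. Make D5's linear-model sentence name that model.
2. Delete D5's six-week exposure sentence and its exclusion of early leavers from the mixed model.
3. Define withdrawal. Replace the sentence on early leavers with a commitment that people who stop the intervention but keep their consent are still invited to the 12- and 24-week tests. Without this step, the first two do nothing about absence at 12 weeks.
4. Use the actual 12-week test as the end-point whenever there is one. Record an early termination test, but do not substitute it in the primary analysis; carry-forward becomes a sensitivity analysis.
5. Keep the six-week set as a labelled sensitivity analysis, define exposure for CTL, and report numbers and reasons for early leaving by arm.

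The cost is wording plus a few home or lab tests already in the schedule. The downside is possible dilution of the effect. At D6's assumptions (unadjusted t-test, SD held at 6.0), power is:

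| Tested | No dilution | 10% of EXP gain nothing | 20% gain nothing |
|---|---|---|---|
| 44 | 90% | 83% | 74% |
| 38 (34 completers plus half of 8 early leavers) | 85% | 77% | 67% |

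If 6 of 22 EXP gain nothing, the difference is 6.0 × 16/22 = 4.36 s and power with 44 tested is 65%. The planned 34 completers give 81%. The case for the change is validity and consistency, not power.
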